2.0 PROPOSED TRIAL RATIONALE

Anti-PD-1 antibodies have demonstrated activity in the treatment of lung cancer. Opdivo was approved in February of 2015 by the FDA for patients with metastatic squamous NSCLC with progression on or after platinum based therapy. In the open-label trial, patients were randomized to receive OPDIVO (n=135) administered at 3mg/kg every 2 weeks. Median survival was improved to 9.2 months compared to 6 months in patients receiving docetaxel (n=137) 75mg/m² every 3 weeks, p=0.00025. Median progression free survival was slightly improved to 3.5 months compared to 2.8 months but 1 year overall survival was improved to 42% compared to 24% (36).

We expect that improvements in local control, increased immunogenic response and abscopal effect seen with combined modality treatment will result in improved local control, progression free survival and resultant significant increases in overall survival beyond 3 months. We propose a pilot/phase II study to assess the safety and efficacy of combination immunotherapy and stereotactic ablative radiation therapy (I-SABR).

Treatment will be a sequential combination treatment of SABR/SBRT and immunotherapy to assess the safety and feasibility of treatment. SABR/SBRT will be administered in 3-5 daily treatments followed by immunotherapy following the conclusion of SABR/SBRT. This approach will take advantage of the transient increase in antigen availability, increased antigen presentation and upregulation of PD-1 by tumor cells following ablative radiation therapy. After an interim safety analysis, the study will continue to the phase II portion where overall survival, progression free survival and response rate will be the primary and secondary end points. For reference, outcomes will be compared to the immunotherapy arms of checkmate 057 and Keynote 042 trials.

Several trials examining combination I-SABR are currently underway. A table of selected studies is included in [Table 1](#).

Study (Institution)	SABR Target	Dose (Gy/Fractionation)	Immunotherapy Agent	Sequence
NCT02239900 (MD Anderson Cancer Center)	Liver Lung Adrenal	50/4 60/10	Ipilimumab	Concurrent/Sequential
NCT01862900 (Chiles Research Institute)	Lung Liver	15/1 201/1	Anti-OX40	Concurrent
NCT01769222 (Stanford University)	Any	20/2	Ipilimumab	Concurrent
NCT02298946 (NIH/NCI)	Liver	8/1 24/3	PD-1 Inhibitor	Sequential

Table 1. List of selected ongoing I-SABR studies

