4.3 Immunotherapy

Immunotherapy will be delivered in the form of PD-1/PD-L1 blockade using approved anti PD-1/PD-L1 agents. Dose reductions are appropriate for toxicity as specified or at the discretion of the treating medical oncologist. Prior immunotherapy as part of multi-drug therapy or monotherapy is acceptable prior to initiation of SBRT.

The DLT observation period for continuation or discontinuation of therapy is defined as 14 days starting with cycle 1, day 1. To be evaluable for DLT, a patient must have received at least the first 2 administrations and be monitored for at least 14 days following the first administration. Any of the below outlined events occurring during each DLT observation period and considered to be at least possibly related to Nivolumab will qualify as a DLT.

Non-Hematologic Toxicity

1. Grade ≥ 2 uveitis
2. Any Grade ≥ 3 non-hematologic toxicity except
 - a. Nausea, vomiting or diarrhea
 - b. Clinically insignificant laboratory abnormalities
 - c. Grade 3 infusion reactions that respond to medical management
 - d. Grade 3 immune related effects other than uveitis that improve within 7-14 days with steroid treatment (Appendix 1).

Hematologic Toxicity

1. Grade 4 neutropenia lasting more than 1 week
2. Grade 4 thrombocytopenia
3. Grade 3 thrombocytopenia with bleeding
4. Grade ≥ 3 febrile neutropenia

Special

1. Grade ≥ 2 pneumonitis

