
• Enterocolitis hemorrhagic
 
 • Gastrointestinal (GI) perforation • Necrotizing colitis 
Diarrhea: Patients who experience diarrhea should be advised to drink liberal quantities of clear fluids. If sufficient oral fluid intake is not feasible, fluid and electrolytes should be substituted via IV infusion.
	
Grade 2
	
Hold until ≤Grade 1. Resume at same dose level. May increase dosing interval by 1 week if it takes more than 4 weeks for toxicities to resolve.
	
GI consultation and endoscopy is recommended to confirm or rule out colitis for grade 2 diarrhea that persists >1 week or grade 1-2 diarrhea with rectal bleeding (additional guidelines for the treatment of persistent colitis are provided below). Grade 2 diarrhea should be treated with the addition of oral diphenoxylate hydrochloride and atropine sulfate four times daily and budesonide 9 mg daily. Grade 2 diarrhea with diffuse ulceration and bleeding seen on endoscopy may require oral steroids with prolonged taper and represent an increased risk for the development of bowel perforation. Consider prophylactic antibiotics for opportunistic infections. When symptoms improve to Grade 1 or less, steroid taper should be started and continued over no less than 4 weeks. • In patients with Grade 2 enterocolitis, IMMUNOTHERAPY should be withheld and anti-diarrheal treatment should be started. If symptoms are persistent for more than one week, systemic corticosteroids should be initiated (eg, 0.5 mg/kg/day of prednisone or equivalent). When symptoms improve to Grade 1 or less, corticosteroid taper should be started and continued over at least 1 month.
	
 • Blood and/or mucus in stool with or without fever • Constipation • Diarrhea • Ileus • Nausea and/or vomiting • Peritoneal signs consistent with bowel perforation • Rectal bleeding • With or without fever 
Patients with diarrhea should be
	
or parasitic infection, viral gastroenteritis, or the first manifestation of an inflammatory bowel disease by examination for stool leukocytes, stool cultures, and a Clostridium difficile titer.

Event(s)	CTCAE v4.03 Grade	Management	Action/Supportive Care Guidelines

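### Section 4.3 exempts diarrhea from the DLT definition at any grade and response, and its two-dose evaluability rule drops patients whose DLT stops dose 2

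*Protocol*

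**What the plan says.** Section 4.3 (Immunotherapy) sets the window and its purpose: "The DLT observation period for continuation or discontinuation of therapy is defined as 14 days starting with cycle 1, day 1". An event in that window counts if it is "considered to be at least possibly related to Nivolumab will qualify as a DLT".

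Under Non-Hematologic Toxicity, item 2 makes every event of Grade 3 or higher a DLT apart from four exceptions. Three of them matter here:

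- Item 2a: "a. Nausea, vomiting or diarrhea"
- Item 2c: "Grade 3 infusion reactions that respond to medical management"
- Item 2d: "Grade 3 immune related effects other than uveitis that improve within 7-14 days with steroid treatment (Appendix 1"

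To be evaluable for DLT, "a patient must have received at least the first 2 administrations" and must be followed for at least 14 days after the first one.

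Appendix I manages Grade 3-4 diarrhea inside its colitis row. The drug is withheld, perforation is ruled out, IV steroids are given, and infliximab is considered if there is no early response.

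**The concern.** Items 2c and 2d each carry two limits: the event must be Grade 3, and it must respond to treatment. Item 2a carries neither. As worded, it therefore removes the most severe drug-related diarrhea from the DLT definition, although Appendix I treats that diarrhea as a colitis-type immune event needing steroids and possibly infliximab. Whether one clinical picture is a DLT then depends on the term written on the form.

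The evaluability rule raises a second problem, which applies to every DLT type. A toxicity serious enough to stop treatment after one dose also takes the patient out of the evaluable group.

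At stake are the DLT classification itself, the individual decision to continue or stop therapy that Section 4.3 links to the DLT period, and the account of tolerability. Section 3.1 makes tolerability part of the pilot's primary objective.

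**Working it through.** The plan states no figure on this point, so there is nothing to reproduce. The check applies the rules as written.

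**Step 1. Is item 2a limited anywhere else?** The hematologic list covers neutropenia, thrombocytopenia and febrile neutropenia. The special list covers pneumonitis only. Neither brings diarrhea back in. Section 7 and Appendix I are rules for dosing and management, and they do not alter what counts as a DLT. Item 2a therefore stands without a limit.

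**Step 2. Classify the same event under each term.** The four exceptions are listed as alternatives, so meeting one is enough. All rows assume an event in the window that is at least possibly related to nivolumab.

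| Event | Recorded as diarrhea | Recorded as colitis |
|---|---|---|
| Grade 3, improves on steroids within 7-14 days | Not a DLT (2a) | Not a DLT (2d) |
| Grade 3, does not improve on steroids | Not a DLT (2a) | DLT (fails 2d) |
| Grade 4 | Not a DLT (2a) | DLT (2d covers Grade 3 only) |

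The two terms agree in the first row and disagree in the other two. Each disagreement runs towards fewer DLTs. The table shows how the rule works. It says nothing about how often such events occur.

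**Step 3. Apply the evaluability rule.** Section 4.3 requires two doses and has no clause for a patient whose DLT comes before the second. Section 7 delays dosing for drug-related non-skin events of Grade 2 or higher, with some exceptions. Appendix I withholds the drug in the Grade 3-4 colitis row and stops nivolumab permanently for Grade 3 enterocolitis. If dose 2 is never given, the patient is not evaluable, whatever the type of DLT.

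**Step 4. Timing.** The only nivolumab interval in the document is the one Section 2.0 reports for the earlier randomized trial: "patients were randomized to receive OPDIVO (n=135) administered at 3mg/kg every 2 weeks". Assuming the same interval here, dose 2 is due on day 1 + 14 = day 15, and the window covers days 1 to 14. On schedule, any event in the window precedes dose 2, so Step 3 can arise for any DLT that leads to stopping.

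**Step 5. How the two parts meet.** If severe diarrhea prevents dose 2, the patient is not evaluable under either term. Correcting item 2a alone would not recover that patient.

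**The case against.** The strongest reply is that nothing turns on the DLT label. DLT is not an objective in Sections 3.1 or 3.2. There is no dose escalation, DLT rate or count threshold. The only cohort rule is Grade 3 or higher pneumonitis above 5%. The pilot is judged over 15 weeks rather than 14 days, and the events are still collected as adverse events (Section 8.2, Appendix III). All of this stands, and it is why the point is minor.

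A second reply is that patients are protected anyway, since Section 7 delays dosing and Appendix I withholds the drug. That largely stands, and Section 4.3 names no separate action that the label triggers. It is not complete, however. For Grade 3-4 diarrhea Appendix I withholds, and it discontinues only if steroids cannot be reduced within 12 weeks. Section 4.3 ties the DLT period to the decision to continue or stop.

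A third reply is that the recommended work-up would often lead to a colitis diagnosis, and that item 2d, which points to the appendix, was meant for immune-related diarrhea. That narrows the gap. But nothing says that item 2d overrides item 2a, and an event left recorded as diarrhea is exempt.

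Finally, the two-week interval comes from the earlier trial, while this protocol refers only to approved or standard dosing. Nor does Section 4.3 require dose 2 to fall inside the window. Both points are correct. A reader might infer from day 15 against day 14 that the evaluability rule contradicts itself. It does not, because a dose on day 15 satisfies it. The defect is confined to patients in whom dose 2 is not given.

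**Conclusion.** The point holds as a minor correction. Item 2a lets Grade 4 diarrhea, and Grade 3 diarrhea not improving on steroids, escape the DLT definition when recorded as diarrhea. The same event recorded as colitis is a DLT. Separately, the two-dose requirement excludes a patient whose DLT after dose 1 stops dose 2, whatever the DLT type.

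No numerical size can be given, because the protocol states neither a DLT rate nor a frequency of such events within 14 days. The consequence is limited to DLT classification, the individual decision to continue or stop, and the pilot's description of tolerability. The conclusion assumes that the exceptions are alternatives and that events are classified by the recorded term.

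Two stronger readings are not supported:

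- A reader might infer that a cohort safety decision is weakened. No such decision uses a DLT count, and the pneumonitis rule is unaffected.
- A reader might infer that the other diagnoses in the Appendix I colitis row, such as gastrointestinal perforation or hemorrhagic enterocolitis, are exempt too. They are distinct diagnoses that item 2a does not name, so it does not exempt them.

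**What to change.** Make three changes to Section 4.3:

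1. Limit item 2a to Grade 3 nausea, vomiting or diarrhea that responds to supportive care.
2. State that diarrhea managed with steroids under the Appendix I colitis row is classified by item 2d. Grade 4 events, and Grade 3 events that do not improve within 7-14 days on steroids, would then be DLTs whichever term is recorded.
3. State that a patient who has a DLT before the second administration counts as DLT-evaluable.

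The cost is one qualifier and two sentences, with no added visits or data. The downside is that slightly more events will be classified as DLTs.

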4.4 Duration of Study

The study will conclude 24 months after the last patient is accrued. Given the poor prognosis and short overall survival in patients with metastatic NSCLC, all end-points should be realized within 24 months. At the conclusion of the study, patients and investigators may decide to continue with Immunotherapy treatment. We expect to enroll 100 patients over 2 years.

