3. STUDY OBJECTIVES

3.1 Primary Objectives

The primary objective of the pilot phase of the study is to characterize the safety, feasibility and tolerability of sequential combination I-SABR in patients with metastatic NSCLC. The first 20 patients will be evaluated for 15 weeks following treatments with I-SABR prior to continuing enrollment. In the Brahmer trial, 5% of patients in the Nivolumab arm developed pneumonitis with a median time to onset of treatment related pulmonary events of 15 weeks. All but one patient with pulmonary events were treated with glucocorticoids and all cases resolved with a median time to resolution of 5 weeks (range 0.6-12.1 weeks).

If more than 5% of patients develop grade ≥ 3 pneumonitis during the initial evaluation phase, no lung directed therapy will be permitted during the phase II portion.

The primary objective of the phase II portion of the study will be overall survival.

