5.3 Sample Size

More than 350 patients with metastatic lung cancer present to the Crozer-Keystone health system for treatment annually. If 50% of patients are eligible for this study, we expect approximately 100 patients will enroll and be treated on this study. Patients will be followed for 2 years on the study. The study will conclude 2 years after the last patient is enrolled. An interim safety and feasibility analysis will be performed on the first 20 patients in the pilot phase. Overall survival, progression free survival, local control and subgroup analysis will be performed on the entire patient cohort at the conclusion of the study.

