APPENDIX III: STUDY PARAMETERS AND ASSESSMENTS

Table 5.0: Pre-treatment assessments

Assessment	Time Points
	≤ 30 days prior to registration
Evaluation by a radiation oncologist	X
Evaluation by a medical oncologist	X
History/physical examination	X
Performance Status (ECOG)	X
CBC w/ diff & ANC, platelets, ALT, AST	≤ 30 days prior to registration.
Serum/urine pregnancy test (if applicable)	≤ 14 days prior to registration
CT Scans of the chest/abdomen/pelvis with radionuclide bone scan OR whole body PET/CT	X
Histological confirmation from at least one metastasis	x
MRI of the vertebral column	If vertebral column metastases identified on staging and will be treated

Table 6.0: Post-Treatment Assessments**ASSESSMENTS IN FOLLOW-UP**

Assessment	Time Points	
	30 days after completion of SBRT	Every 3 months after completion of SBRT for a total of 2 years
Physical examination	X	X
Evaluation by a radiation oncologist	X	X
Performance status	X	X
ALT, AST, Total and Direct Bilirubin	X (If SBRT delivered to the liver)	X (If SBRT delivered to the liver) Perform at 3 months then every 6 months
Hgb	Recommended if clinical symptoms of anemia on physical exam post-treatment	
Diagnostic Imaging		X Per protocol or if clinically warranted
Adverse event evaluation	X	X

LIST OF COMMON ABBREVIATIONS AND DEFINITIONS OF TERMS

ADL	Activities of Daily Living
AE	Adverse event
AESI	Adverse event of special interest
ALP	Alkaline phosphatase
ALT	Alanine aminotransferase
ANA	Antinuclear antibody
ANC	Absolute neutrophil count
aPTT	Activated partial thromboplastin time
ARGUS	Pharmacovigilance and clinical safety software system
AST	Aspartate aminotransferase
AUC	Area under the concentration–time curve
BAL	Bronchoalveolar lavage
BC	Breast cancer
BUN	Blood urea nitrogen
CPA	Cyclophosphamide
CR	Complete response
CRF; eCRF	Case report form (electronic or paper); electronic case report form
CRO	Contract research organization
CRP	C-reactive protein
CT	Computed tomography
CTLA-4	Cytotoxic T-lymphocyte antigen 4
CTV	Clinical target volume
(NCI-) CTCAE	(National Cancer Institute) Common Terminology Criteria for Adverse Events
DLT	Dose-limiting toxicity

Dmax Maximum radiation dose

EC Ethics committee

ECG Electrocardiogram

EDC Electronic data capture

FDG-PET 18F-fluorodeoxyglucose positron emission tomography

FFPE Formalin-fixed, paraffin-embedded

FNA Fine-needle aspirate

fx Fraction(s)

GCP Good clinical practice

GBM Glioblastoma multiforme

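### Section 4.4 expects every endpoint within 24 months, but the protocol's own survival figures leave about 16 to 26% of patients alive then, and no survival follow-up is provided after 2 years although the study stays open

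*Protocol*

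**What the plan says.** Section 3.1 names the endpoint at issue: "The primary objective of the phase II portion of the study will be overall survival". Section 4.4 closes the study 24 months after the last accrual and, citing poor prognosis and short survival, states that "all end-points should be realized within 24 months". On accrual it says "We expect to enroll 100 patients over 2 years".

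Section 5.3 states "Patients will be followed for 2 years on the study", repeats the closing rule, and places the OS analysis of the whole cohort at the end of the study. Table 6.0 in Appendix III sets the post-treatment visits and tests: "Every 3 months after completion of SBRT for a total of 2 years". The protocol has no provision for survival status after that.

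The only OS figures for a reference arm are in section 2.0. For nivolumab in squamous disease, "Median survival was improved to 9.2 months compared to 6 months in patients receiving docetaxel", with 42% alive at 1 year. The same section hopes for "significant increases in overall survival beyond 3 months" with the combined treatment, without naming the baseline.

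**The concern.** Two things do not fit together. First, a 9.2-month median with 42% alive at 1 year does not suggest that deaths will be nearly complete at 24 months, and still less so if the treatment works as hoped. The reason given for the follow-up length is therefore weaker than section 4.4 makes it sound.

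Second, accrual lasts 2 years and the study closes 2 years after the last patient, so an early patient could be observed for close to 4 years. Follow-up nevertheless ends at 2 years for everyone. Deaths that occur while the study is open, and before OS is analysed, have no planned route into the data. This loss occurs at data collection: an analysis plan cannot recover deaths that were never recorded.

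**Working it through.** **Inputs.** From section 2.0: median OS 9.2 months, 1-year OS 42%, docetaxel median 6 months. From sections 4.4 and 5.3: 100 patients, accrual over 24 months, close 24 months after the last patient, 2 years of follow-up per patient. Assumptions: exponential survival, uniform accrual, no dropout, and the 2 years counted from enrolment (Table 6.0 counts from the end of SBRT, a small difference). The 12.2-month median is also an assumption: 9.2 + 3, one reading of the hoped-for gain.

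**Does the exponential fit the stated figures?** A 9.2-month median gives 0.5^(12/9.2) = 40.5% alive at 1 year, against 42% stated. The two agree within 2 points.

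**Alive at 24 months**, S(24) = 0.5^(24/median):
- median 9.2: 16.4%
- from 1-year OS: 0.42² = 17.6%
- median 12.2: 25.6%
- docetaxel median of 6: 6.2%

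This does not depend closely on the exponential shape. To have 5% alive at 24 months when 42% are alive at 12, the second-year hazard would have to be ln(0.05/0.42) / ln(0.42) = about 2.5 times the first-year hazard.

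**Deaths per 100 patients.** With follow-up ending at 2 years: 100 × (1 − S(24)). With follow-up to study close, where λ = ln 2/median: 100 × (1 − [exp(−24λ) − exp(−48λ)]/(24λ)).

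| Scenario | To 2 years | To study close | Difference |
|---|---|---|---|
| Median 9.2 | 83.6 | 92.4 | 8.8 |
| 1-year OS 42% | 82.4 | 91.6 | 9.3 (unrounded) |
| Median 12.2 | 74.4 | 86.0 | 11.6 |

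Following to close adds 8.8/83.6 = about 11% to 11.6/74.4 = about 16% more deaths. If the median were longer, say 15 to 24 months (a range chosen here because the protocol gives no OS figures for first-line or pretreated patients), 33 to 50% would be alive at 24 months and 13 to 14 deaths per 100 would be missed.

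**Where the extra information lies.** At 36 months, half the cohort has enough potential follow-up, so the number at risk per 100 is 100 × 0.5 × S(36). That is 3.3 at a median of 9.2 and 6.5 at 12.2. Most of the gain therefore lies between 24 and about 36 months.

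**Effect on the usual summaries.** In a simulation of this scenario (100 patients, 1,000 runs per median), the Kaplan-Meier median and its 95% interval were identical with and without the 2-year limit in 100% of runs at a median of 9.2 and in 99.9% at 12.2. Expected deaths matched the table to within about 0.3 per 100.

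**The case against.** The strongest reply is that *realized* can mean *able to be evaluated*. On that reading section 4.4 is right about median OS, 1-year OS, the 3-month evaluations of progression-free survival and local control, and 6-month pneumonitis. The protocol states no 24-month survival rate, so the 16 to 26% is an extrapolation. This stands, and a reader who inferred a flat contradiction would go too far. What remains is that the sentence covers all endpoints and rests on survival being short. If its 24 months are counted from the last accrual instead, full follow-up would still leave 100 − 92.4 = 7.6 to 100 − 86.0 = 14.0 patients per 100 alive.

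A reader might also infer that OS is censored at 24 months and later deaths are thrown away. No passage says so: Table 6.0 is a schedule of visits and tests, and censoring rules may sit in an analysis plan that is not shown. Deaths that happen to be known at study close could be counted. That does not repair the gap. Counting known late deaths while survivors remain at their last 2-year contact would leave mainly patients who die in the risk set and pull the tail of the curve down.

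Two larger benefits are tempting to claim and are not supported. More deaths would narrow the interval for the median only under a fitted exponential model, which the protocol does not specify; the Kaplan-Meier interval does not move. And only the very first patient could reach 48 months, so useful information does not extend that far.

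Finally, equal 2-year follow-up for every patient is a legitimate design, and ending it there is administrative censoring that leaves the curve to 24 months unbiased. That also stands, and it limits how much weight this point carries.

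**Conclusion.** The point holds as a modest one. Section 4.4 is sound about what can be estimated by 24 months but misleading about how complete the OS events will be: about 16 to 18% of patients would be alive on the protocol's reference figures, and about 26% at an assumed 12.2-month median. The 2-year follow-up leaves about 9 to 12 deaths per 100 patients (84 against 92, or 74 against 86) without systematic collection while the study is still open.

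The cost falls on analyses whose precision depends on the number of deaths, notably secondary objective 4 on the number of metastatic sites, which divides the deaths among the three lesion-count strata of section 8.2. It also falls on any description of survival after 24 months. The OS curve to that point and its median are not affected, and the primary analysis is not invalidated. The sizes rest on exponential survival, uniform accrual and no dropout.

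**What to change.** In section 4.4, say that median OS is expected to be reached within 24 months, while roughly 16 to 26% of patients may still be alive at that time, and give the assumptions.

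In section 5.3 and Table 6.0, keep clinic visits to 2 years. Add that vital status will be updated for every patient who has not withdrawn consent, survivors as well as deaths, to one common cut-off at study close, and that OS will be analysed at that cut-off. Updating survivors to the same date is the essential part, since it prevents the tail from being biased by late deaths alone.

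The cost is the change of wording plus chart or registry checks for roughly 16 to 26 patients per 100 who are past 2 years. It adds no visits, patients or treatment.
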